The study is observational, retrospective-prospective, multicenter "real-life" study involving 26 centers belonging to the SEIFEM group. Regarding the retrospective part, clinical data will be collected on all patients with LMA FLT3+ (ITD or TKD mutation) treated with Gilteritinib from when the drug was approved and marketed in Italy (April 2, 2020) until April 30, 2022. Enrollment in the prospective cohort will have an estimated duration of 24 months from the time of study approval. Patients enrolled in the last month will be followed for six months from the date of enrollment to check for the occurrence of any infections. For each case of a patient receiving salvage monotherapy with Gilteritinib, a control patient with LMA R/R FLT3+ on salvage chemotherapy should also be included.

Study Duration.

Relative to the prospective part, the study will have a total duration of 24 months from the first patient enrolled and six months of observation from the last patient enrolled.

Population

Inclusion criteria:

- All patients with FLT3+ relapsed/refractory AML to any line of therapy treated with Gilteritinib
- Patients ≥ 18 years of age
- Signature of appropriate informed consent

Exclusion criteria:

- Patients < 18 years old

Study Objectives.

The purpose of the present retrospective/prospective study is to evaluate the "real life" incidence of infectious complications in patients with relapsed/refractory FLT3+ AML treated with Gilteritinib.

Primary objective

To assess "real-life" in patients with relapsed/refractory FLT3+ LMA treated with Gilteritinib the absolute infectious risk and compare it with relapsed/refractory patients receiving chemotherapy.

Secondary objectives.

- To assess the site, incidence and outcome of bacterial/fungal/viral infections in this patient setting
- To assess the need for hospitalization and the duration of hospitalization
- To analyze the different antifungal prophylaxis policies in different Hematology Centers and correlate them with the incidence of infection
- To analyze the incidence of side effects related to the use, in combination with Gilteritinib, of antifungal/antibacterial/antiviral drugs (in prophylaxis/therapy).

Methods

The proposed study is retrospective-prospective, multicenter, observational.

Data will be retrospectively collected from all cases observed from April 2, 2020 until April 30, 2022 about the infectious event and related treatment information (database attached).

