In the prospective cohort, enrollment will have an estimated duration of 24 months from the time of study approval. Patients enrolled in the last month will be followed for six months thereafter to check for the occurrence of any infections.

Data from patients with gilteritinib monotherapy and data from patients for whom the clinician's choice is the use of chemotherapy (consisting, for example, of the following regimens: FLA-IDA, MICE, MEC, intermediate/high-dose cytarabine) will have to be analyzed to assess the infectious risk associated with gilteritinib monotherapy.

It is reiterated that since this is an observational study, the choice of therapy is at the discretion of the treating hematologist and independent of enrollment in this study.

Informed consent will be sought from all patients still alive at the time of initiation of data collection and from patients whose data will be collected prospectively. However, it should be noted that since this is a study that mainly considers patients with relapsing hemopathies that could be complicated by life-threatening infections, the rate of obtainable consents may be reduced due to the mortality of these hemopathies.

The incidence of infection will be related to the following variables:

- Age
- Sex
- Comorbidities
- Type of antimicrobial prophylaxis performed
- Type of FLT3 mutation (ITD vs TKD)
- Type of response to treatment
- Hospitalization and duration

Any side effects related to the combination of Gilteritinib with antimicrobial drugs used in prophylaxis/therapy by different centers will also be evaluated.

The study will not affect normal care practice in any way, as there is no blood sampling for patients. Each patient and each control will be assigned an identification code that will allow the omission of any reference that would allow patient recognition.

Clinical information will pertain to the coordinating center and will be collected within a database.

Based on the following considerations:

- it is assumed that the reference population, or target population from which the sample is drawn (78 patients), is Gaussian distributed with unknown variance;
- the null hypothesis (superposibility of the two populations: sample and target) is rejected if the sample mean differs from the mean value of the reference population by an amount, in absolute value, equal to or greater than 36.7 percent of the standard deviation;

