- we adopt, for testing the hypotheses (null and alternative), the two-tailed Gauss z-test with $\alpha = 0.05$ (error of the first kind) and $\beta = 0.10$ (error of the second kind), which implies, as is well known, a test power of 90%;

at least 78 patients are expected to be enrolled.

The analysis will be aimed at evaluating the distribution of infectious events (viral/bacterial/fungal) and identifying parameters that significantly influence the outcome of infectious complication.

With regard to descriptive statistical analyses, central tendency, variability, symmetry and kurtosis will be calculated, all accompanied by appropriate graphical representations; with regard to inferential analyses, in addition to multivariate binary logistic regression, parametric and nonparametric hypothesis testing will be carried out, respectively, for quantitative variables with parametric tests such as: Student's t-test, Fisher's F-test, etc. and for categorical variables by nonparametric tests such as: chi-square, Mann Whitney's U, Fisher's exact test, etc. Only results with p-values ≤ 0.05 will be considered statistically significant.

The study does not involve any expenses related to data collection or additional examinations.

Italian Hematology Centers belonging to the SEIFEM Group, which includes both university and hospital facilities, will participate in the study (Appendix 1: list of participating centers).

Data collection and analysis and report preparation will be the responsibility of the scientific board.

Dissemination of results

Publication of results in leading international scientific journals dealing with topics related to hematology and infectious diseases. Also, presentation of results at major national and international hematology congresses, (American Society of Hematology, European Hematology Association, Italian Society of Hematology)

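### The 78-patient, 90%-power calculation is for a one-sample test; the primary comparison of gilteritinib with chemotherapy has no sample-size justification

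*Combined protocol and SAP*

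**What the plan says.** The only sample-size reasoning is the list of considerations towards the end of Methods. It states that "it is assumed that the reference population, or target population from which the sample is drawn (78 patients), is Gaussian distributed with unknown variance". Rejection of the null hypothesis follows "if the sample mean differs from the mean value of the reference population" by at least 36.7% of the standard deviation. The test is a two-tailed z-test with alpha 0.05 and beta 0.10, "which implies, as is well known, a test power of 90" per cent. The conclusion is that "at least 78 patients are expected to be enrolled".

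The primary objective has two parts: to assess the absolute infectious risk on gilteritinib and to "compare it with relapsed/refractory patients receiving chemotherapy". Study design adds that for each gilteritinib monotherapy case "a control patient with LMA R/R FLT3+ on salvage chemotherapy should also be included". Methods says that data from both groups will be analysed, and refers to them separately: "Each patient and each control will be assigned an identification code". The inferential analysis consists of general parametric and nonparametric tests, including chi-square and Fisher's exact test, "in addition to multivariate binary logistic regression".

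**The concern.** The calculation and the primary comparison are different problems. The calculation sets one sample mean against a fixed mean of the population from which the sample is said to be drawn. It mentions no chemotherapy group, infection risk, allocation ratio or between-group difference, and the documents give no reference mean. The primary comparison sets one estimated risk against another. For independent groups of equal size, that doubles the variance of the difference.

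It is also unclear whether 78 is the gilteritinib group or the total. The text favours 78 gilteritinib patients plus controls, because the inclusion criteria cover only gilteritinib-treated patients and the control is an addition to each case. It does not say so outright.

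What is at stake is how the result is read. With significance judged at p ≤ 0.05 and 90% power stated, a non-significant comparison would naturally be taken as evidence of similar infection risk. In fact, differences near 20 percentage points could be missed. The descriptive part of the objective has no stated precision either.

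**Working it through.** **Inputs from Methods:** two-sided alpha 0.05 (z = 1.960), power 90% (z = 1.2816), difference d = 0.367 SD, n = 78. **From Study design:** one control per case.

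**1. The plan's own figure.** One-sample z-test:

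n = ((1.960 + 1.2816) / 0.367)² = 78.01

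Power at 78 = Φ(0.367 × √78 − 1.960) = 90.0%. The plan's 78 is reproduced, provided 0.367 SD is read as the true difference to detect. Taken literally as the rejection threshold, it would give alpha of about 0.001 and 50% power.

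**2. The same d with two independent groups of n each.**

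n per group = 2 × 78.01 = 156.02, rounded up to 157

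Power = Φ(0.367 / √(2/n) − 1.960)

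| n per group | Power |
|---|---|
| 39 (78 in total) | 37% |
| 78 | 63% |
| 100 | 74% |
| 150 | 89% |
| 157 | 90% |

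**3. If the controls were matched.** With 78 pairs and within-pair correlation r, power = Φ(0.367 / √(2(1 − r)/78) − 1.960). This is 73% at r = 0.2 and 90% at r = 0.5.

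**4. On the risk scale.** The documents give no overall infection rate. The 45.9% in the background is grade ≥ 3 febrile neutropenia, and the 25% is invasive fungal infection. Base risks of 25–50% are therefore my assumption. Over that range, 0.367 SD (SD taken from the average of the two binomial variances) is about 14 to 18 points.

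Difference in percentage points detectable with 90% power, two-sided 0.05 (increase / decrease from the base risk):

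| Base risk | 78 + 78, pooled z | 78 + 78, Fisher | 39 + 39, pooled z | 39 + 39, Fisher |
|---|---|---|---|---|
| 25% | 24.8 / 18.6 | 25.9 / 19.1 | 35.4 / 24.0 | 37.7 / 24.2 |
| 35% | 25.6 / 21.9 | 27.2 / 22.6 | 35.7 / 28.9 | 37.8 / 29.5 |
| 50% | 24.8 / 24.8 | 25.7 / 25.7 | 33.7 / 33.7 | 35.5 / 35.5 |

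The Fisher columns come from exact enumeration. Power for a 15-point difference by the pooled z-test is 47–70% at 78 + 78 and 26–41% at 39 + 39. With Fisher's exact test it is lower, about 39–63% and 20–32%.

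**5. Precision of the absolute risk.** 95% CI half-width = 1.96 × √(p(1 − p)/n). For p of 25% and 50% this is 9.6 and 11.1 points with n = 78, and 13.6 and 15.7 points with n = 39.

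**The case against.** The best defence is that the plan never names 0.367 SD as the gilteritinib-versus-chemotherapy difference of interest, so 63% is not the power of anything the plan promises. That is fair. The figure is illustrative and holds only for 78 + 78 independent, unmatched, unadjusted patients. The firm statement is that no power is given for the comparison at all.

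One could also take the reference population to be chemotherapy patients with a known mean. No such mean appears, the sample is said to come from that population, and enrolling controls one to one shows that their risk will be estimated.

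Three further points carry some weight:

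- **78 is a minimum.** The study takes all retrospective cases plus 24 months of prospective enrolment at 26 centres, so it may well be larger. But no larger target is stated, and 100 + 100 reaches only 74%.
- **Matching could recover power.** This needs a within-pair correlation of about 0.5, and the plan states no matching factors and no paired analysis.
- **The binary endpoint is inferred.** The plan does not say whether risk means patients with at least one infection or a rate of events. Absolute risk and binary logistic regression support the binary reading.

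Finally, treatment is the clinician's choice, so the comparison will need adjustment, and adjusted power may differ from these figures. None of this makes the stated 90% apply to the primary comparison.

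**Conclusion.** The concern holds and should be fixed before the plan is relied on. The figure of 78 is correct for a one-sample z-test, but the plan's only power statement does not belong to its primary comparison. At the stated minimum and the same standardised difference, power is 63% rather than 90% on the reading that favours the sponsor, and 37% if 78 is the total. On the risk scale, the comparison has 90% power only for differences of about 19 to 26 points (24 to 36 with 39 + 39) by the pooled z-test, and slightly larger ones with Fisher's exact test.

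These sizes assume independent groups of equal size, no matching or covariate adjustment, a binary endpoint and base risks of 25–50%. The mismatch itself depends on none of these assumptions.

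**What to change.** State whether 78 is the gilteritinib group or the total, and say that infection risk is analysed as a proportion of patients if that is the intention. Then replace the one-sample paragraph with a two-proportion statement, for example:

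> At the minimum size of 78 + 78 unmatched patients, the unadjusted comparison has 90% power for a risk difference of about 19 to 26 percentage points, depending on direction and on the assumed base risk (25–50%). Power for a standardised difference of 0.367 SD is 63%.

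If 78 is the total, the corresponding figures are about 24 to 36 points and 37%.

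Present this as what the available number can detect, not as a target, and note that the adjusted analysis may have different power. If controls are to be matched, name the matching factors and the paired analysis.

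Two additions would help: a sentence on whether a difference of that size is clinically relevant, and the precision of the absolute risk (95% CI half-width about 10–11 points with 78 patients, 14–16 with 39).

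The cost is one rewritten paragraph, with no extra patients and no change to data collection. The drawback is a less favourable stated power.

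### The 90% power at 78 patients is computed for one Gaussian mean, while the primary objective compares an infection risk between two groups; the plan states no risk or percentage-point difference, and the same shift has far less than 90% power in that comparison

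*Combined protocol and SAP*

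**What the plan says.** The sample-size bullets in Methods assume that the reference population "is Gaussian distributed with unknown variance". The comparison is whether "the sample mean differs from the mean value of the reference population" by an amount "equal to or greater than 36.7 percent of the standard deviation". The test is a "two-tailed Gauss z-test" with alpha 0.05 and beta 0.10, "which implies, as is well known, a test power of 90" percent. The result is at least 78 patients. The bullets do not name the variable being averaged.

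The primary objective, under Study Objectives, is "the absolute infectious risk" in patients treated with gilteritinib, compared with chemotherapy patients. Study design asks for one chemotherapy control per gilteritinib case. The analysis paragraph in Methods lists binary logistic regression, chi-square and Fisher's exact test, alongside t-tests for quantitative variables. No expected infection risk in either group, no reference value and no difference in percentage points appears anywhere. The plan also does not say whether 78 is the gilteritinib group or the total.

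**The concern.** A risk analysed by logistic regression is a proportion. Its SD is √(p(1−p)), so the variance is fixed by the risk and changes between null and alternative. A Gaussian variable with a separate unknown variance is the wrong model. An effect given only in SD units also hides the size of the difference the study can detect. In addition, the calculation compares one sample with a fixed reference value, while the objective compares two groups of patients.

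The 90% is the only operating characteristic the plan states. If it does not apply to the primary comparison, an ethics reviewer cannot judge whether 78 is adequate. A non-significant result could also be misread as evidence that the infection risks are similar.

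**Working it through.** **Inputs.** From Methods: effect 0.367 SD, two-sided alpha 0.05 (z = 1.960), power 90% (z = 1.282), n = 78. From Study design: one control per case. The reference risks p0 below are assumptions. Two of them, 25% (invasive fungal infection) and 45.9% (grade ≥ 3 febrile neutropenia), are quoted in the background, but neither is an all-infection risk.

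**1. The plan's own figure.** One-sample mean: n = ((1.960 + 1.282)/0.367)² = 78.01. Power at 78 is Φ(0.367·√78 − 1.960) = Φ(3.241 − 1.960) = 90.0%. The arithmetic reproduces, but only as a one-sample two-sided test. Read literally as a rejection threshold, 0.367 SD would give alpha of about 0.0012, so it is taken here as the effect to detect. If the variance is truly unknown, a t-test needs 80 patients and has 89.3% power at 78, a trivial gap.

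**2. The effect in percentage points.** The shift is 0.367·√(p0(1−p0)). At 25%: 0.367 × 0.433 = 15.9 points.

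**3. One-sample power for a proportion at n = 78** (increase / decrease by that shift):

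| p0 | Shift (points) | z-test, score form | Exact binomial |
|---|---|---|---|
| 20% | 14.7 | 86.1 / 97.7% | 80.0 / 97.7% |
| 25% | 15.9 | 89.4 / 97.6% | 84.4 / 95.1% |
| 30% | 16.8 | 87.3 / 95.4% | 87.3 / 95.4% |
| 40% | 18.0 | 90.5 / 92.4% | 86.1 / 92.4% |
| 45.9% | 18.3 | 90.5 / 93.2% | 90.5 / 89.4% |
| 50% | 18.4 | 92.0 / 92.0% | 87.8 / 87.8% |
| 60% | 18.0 | 92.4 / 90.5% | 92.4 / 86.1% |

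**4. Two groups, still Gaussian.** Power is Φ(0.367·√(m/2) − 1.960), with m per group. For m = 39: Φ(1.621 − 1.960) = 36.7%. For m = 78: Φ(2.292 − 1.960) = 63.0%. For 90% power: 2 × 78.01 = 156.02, so 157 per group. Most of the loss therefore comes from the second group, not from the Gaussian form.

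**5. Two proportions.** Power is Φ((D − 1.960·se0)/se1), where D is the shift, se0 uses the pooled risk and se1 the separate risks; no continuity correction. At 25% versus 40.9% with 39 per group, the pooled risk is 0.3295. Then se0 = √(0.3295 × 0.6705 × 2/39) = 0.1064 and se1 = √((0.1875 + 0.2417)/39) = 0.1049. Power is Φ((0.1589 − 0.2086)/0.1049) = Φ(−0.474) = 31.8%.

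| p0 | 39 vs 39 (up / down) | 78 vs 78 (up / down) | Per group for 90% (up / down) |
|---|---|---|---|
| 25% | 31.8 / 46.2% | 56.1 / 75.6% | 182 / 116 |
| 45.9% | 36.6 / 38.6% | 63.4 / 66.1% | 154 / 144 |
| 50% | 37.6 / 37.6% | 64.7 / 64.7% | 149 / 149 |

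At these three risks, the difference detectable with 90% power is about 24 to 35 points with 39 versus 39, and about 19 to 25 points with 78 versus 78.

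**The case against.** The strongest defence is that the mean of a yes/no variable is roughly normal at n = 78, so the Gaussian shortcut is tolerable. This largely stands. With the plan's z-test in score form, one-sample power stays between 86% and 98% over assumed risks of 20–60%. The lower exact-binomial figures partly reflect a conservative test, whose actual size is 3.1–4.7% over that range.

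Three stronger readings are tempting and should be resisted.
- A reader might infer that 90% holds only near a reference risk of about 46%. It does not: the score-form z-test reaches at least 90% in both directions at 40%, 45.9%, 50% and 60%, and the exact test gives 92.4% for an increase from 60%.
- A reader might infer that the z-test inflates type I error, because its actual size at 25% is 6.6%. That is the highest value on the grid; it is 4.6% at 20%, 4.7% at 30%, 4.9% at 40% and 5.3% at 45.9%. This reflects the discreteness of the binomial rather than a systematic fault.
- A reader might restate the one-sample result in points, such as 84% power for 25% versus 41%. That would mislead, because in the two-group comparison the same pair has only about 32% or 56% power with 39 or 78 per group.

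It is also fair to say that the plan never defines the outcome as yes/no. That is inferred from the word risk and the logistic model. Infection counts, the obvious alternative, would not be Gaussian either.

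**Conclusion.** The concern holds in a limited form. The number 78 is computed correctly from its inputs, but the model behind it does not match the primary objective. Because the plan gives no risks, its effect size cannot be read in percentage points. The Gaussian form by itself moves one-sample power modestly, to about 86–98% in score form or 80–98% with an exact test.

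The 90% clearly fails for the gilteritinib versus chemotherapy comparison. For an increase of the same size from assumed risks of 25–50%, power is about 32–38% with 39 versus 39 and 56–65% with 78 versus 78. For a decrease it is higher but still at most 46% and 76%. These figures assume a yes/no outcome, equal groups, an unadjusted comparison and reference risks that the plan does not supply.

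**What to change.** In Methods, delete the bullets on the Gaussian population and the SD-based difference, and replace the power statement with one for two proportions. It should:
- name the primary variable;
- give the assumed infection risk in each group and its source;
- give the target difference in percentage points;
- give the number per group, saying whether 78 is the gilteritinib group or the total;
- name the test;
- give the resulting power, or the difference detectable at 90% power.

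Keep the planned enrolment and restate what it can detect. Do not carry one-sample power figures into the new text. The cost is a few reworded sentences and a less favourable stated power; the rewording itself requires no additional patients or data.

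### The primary absolute infection risk has no stated time zero or horizon, and the named tests take no account of unequal follow-up or censoring

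*Combined protocol and SAP*

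**What the plan says.** The Primary objective section sets out to assess "the absolute infectious risk and compare it with relapsed/refractory patients receiving chemotherapy". For each gilteritinib case, the Study design section says that "a control patient with LMA R/R FLT3+ on salvage chemotherapy should also be included".

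Follow-up is described in three places:

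- Study design: "Patients enrolled in the last month will be followed for six months from the date of enrollment". Methods repeats this for the prospective cohort.
- Study Duration, prospective part: "a total duration of 24 months from the first patient enrolled and six months of observation from the last patient enrolled".
- Methods, retrospective part: "Data will be retrospectively collected from all cases observed from April 2, 2020 until April 30, 2022". Study design ties this window explicitly to patients treated with gilteritinib. No window is stated for retrospective controls.

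On analysis, Methods says: "with regard to inferential analyses, in addition to multivariate binary logistic regression, parametric and nonparametric hypothesis testing will be carried out". It then names Student's t, Fisher's F, chi-square, Mann-Whitney U and Fisher's exact test, and both lists of tests end in an open-ended etc. Methods refers to an attached database, which is not in the text supplied.

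**The concern.** An absolute risk is a probability over a stated interval from a stated origin. The text does not say whether a patient's clock starts at treatment, relapse or enrollment, when it stops, or at what time the risk is read. The six-month rule is a minimum for some patients and is not linked to the primary comparison.

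A chi-square test or logistic model on infected yes/no treats a patient seen for six months and one seen for thirty as equally informative. The result is not the risk at any particular time, and it cannot be set beside a risk from another series. With no horizon fixed in advance, it could also be chosen after the data are seen.

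Death adds to the problem. The Background section cites 12-month survival of 37% on gilteritinib and 19% on salvage chemotherapy, so many patients will die before any long horizon, and possibly at different rates in the two groups.

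**Working it through.** **The plan's own figure.** The target of 78 comes from a one-sample two-sided z-test with effect 0.367 SD, alpha 0.05 and power 90%: ((1.960 + 1.282)/0.367)² = 78.01. It reproduces. The formula contains no event rate, follow-up time or censoring, so it cannot supply the missing horizon. Whether it suits a two-group comparison is a separate finding and carries no weight here.

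**Follow-up range.** In the prospective part, the first enrollee can be followed for 24 + 6 = 30 months and the last for 6. The retrospective window is 758 days, or 24.9 months.

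**Inputs for the illustration.** The documents give 12-month survival of 37% and 19%. If death hazards are constant (assumption), μ = −ln(OS)/12:

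- gilteritinib: −ln(0.37)/12 = 0.0829 per month
- chemotherapy: −ln(0.19)/12 = 0.1384 per month

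The documents give no infection hazard. I assume λ = 0.05, 0.08 and 0.15 per month. Cumulative incidence of first infection with death competing is CIF(t) = λ/(λ+μ) × [1 − exp(−(λ+μ)t)].

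**Effect of observation length.** Example with λ = 0.05 and the gilteritinib μ: CIF(6) = 0.376 × (1 − 0.451) = 20.7%; CIF(12) = 30.0%; shift 9.3 points. If λ is multiplied by f after month six, the shift is exp(−6(λ+μ)) × CIF(6; fλ, μ). Shifts in points for λ = 0.05, 0.08, 0.15:

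| Infection hazard after month six | Gilteritinib μ | Chemotherapy μ |
|---|---|---|
| Unchanged | 9.3, 11.5, 12.0 | 5.8, 7.2, 7.6 |
| Halved | 5.0, 6.4, 7.2 | 3.1, 4.0, 4.5 |
| Quartered | 2.6, 3.4, 4.0 | 1.6, 2.1, 2.5 |

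**Effect of dropping patients with unknown six-month status.** Assume that April 30, 2022 closes follow-up, that treatment starts are evenly spread, and that both groups share the window. Potential follow-up is then uniform on 0 to T = 24.9 months, and 6/24.9 = 24% of patients have less than six months of it. With h = λ+μ:

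- fraction dropped as event-free and censored: (1 − exp(−6h))/(hT)
- fraction observed infected by six months: (1 − 6/T) × CIF(6) + (1/T) × ∫₀⁶ CIF(c) dc
- complete-case risk: fraction observed infected/(1 − fraction dropped)

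| λ | Gilteritinib: complete-case vs true | Chemotherapy: complete-case vs true | Error in the difference |
|---|---|---|---|
| 0.05 | 22.2 vs 20.7% | 18.9 vs 18.0% | 0.6 points |
| 0.08 | 32.5 vs 30.6% | 28.0 vs 26.8% | 0.7 points |
| 0.15 | 50.5 vs 48.5% | 44.1 vs 42.8% | 0.7 points |

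The fraction dropped is 11.5% to 16.6%. Each group's risk is too high by 1.0 to 2.0 points before rounding, but most of this cancels in the difference.

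**Effect of survival at a common horizon.** With equal infection hazards, the true six-month columns above still differ, by 2.7, 3.9 and 5.7 points, because patients on gilteritinib live longer and so stay at risk longer.

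**The case against.** The strongest reply is that no documented mechanism biases the comparison by the amounts shown. A reader might infer that the plan builds in a 6 to 12 point error between groups. That would need one group watched for twelve months and the other for six. The documents do not say this, and nothing exempts controls from the follow-up described for enrolled patients. The objection stands: those figures show how far a crude risk depends on observation length, and no more.

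The retrospective calculation is also conditional. The April 2022 date reads naturally as the end of inclusion, no section says that records stop there, and the window is not stated for controls. Even under those assumptions the difference moves by only 0.6 to 0.7 points, against a standard error of about 6 to 8 points with 78 per group, or 9 to 11 with 39 (group sizes assumed). This also stands.

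The gap may be partly filled elsewhere. The attached database may hold the dates or define a window, the range of 6 to 30 months is what the schedule permits and not a stated intention, and the open-ended test lists leave time-to-event methods unnamed, not excluded. All of this is fair. Still, recording dates does not state which risk is to be estimated, and an unnamed method has not been prespecified.

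Finally, a crude proportion is a valid absolute risk at one common horizon with complete follow-up. That is correct, but the text sets no such horizon and does not assure complete follow-up.

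**Conclusion.** The concern holds in a limited form. The primary quantity is a risk with no common origin or horizon in the text supplied, potential follow-up is unequal, and no named method takes account of that. A crude ever-infected proportion produced under the plan would not be an absolute risk at any stated time.

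With constant death hazards from the cited 12-month survival and assumed infection hazards of 0.05 to 0.15 per month, doubling observation from six to twelve months raises the crude risk by about 6 to 12 points, or about 2 to 7 if the infection hazard falls to a half or a quarter after month six.

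Two stronger readings are not supported. The documents do not show that the group comparison is biased by these amounts. Nor is a difference that arises because one group survives longer an error: at a common horizon it is a true difference in absolute risk, though it must not be read as a difference in infection rate.

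This should be fixed before analysis. It does not by itself invalidate the study.

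**What to change.** Add to the analysis paragraph:

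1. Time zero is the first day of gilteritinib or of salvage chemotherapy, in both cohorts and both groups.
2. The primary estimate is the six-month cumulative incidence of first infection with death as a competing event (Aalen-Johansen, 95% CI), per group and as the difference. Patients with shorter follow-up are censored.
3. Where observation begins after treatment starts, infections are collected back to the first treatment day, or entry is handled as delayed (left truncation). This is needed because the plan counts its six months from enrollment.
4. Infections count regardless of later change of therapy or transplant, or another analysis rule for these events is stated.
5. A cause-specific hazard ratio, or events per patient-month, is reported alongside, to separate infection rate from survival.
6. Logistic regression on six-month status is used only if that status is essentially complete or censoring is weighted for, because dropping event-free censored patients is selective.

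Six months is a choice. It is proposed because it is the only follow-up interval the plan names.

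The cost is analysis wording and four dates per patient: treatment start, first infection, death and last contact. The database may already hold them. Infections after six months become a secondary description. Retrospective patients starting after about October 2021 may be censored early unless their records are read past April 30, 2022.
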